6.9.3. Analysis of tertiary objective: natural decay of maternal neutralizing antibodies

The analysis will be based on total sub-cohort subject with blood sampling at month 2, 4, 6, and 12 for this objective.

The decay of maternal antibody levels over time will be analysed graphically and by a linear regression of the log of maternal antibody levels. A true, natural decay curve will be explored by stochastically reducing the sample to uninfected subjects only. The following steps will be taken to identify, confirmed and suspected infected subjects to eliminate these from the sample;

STEP 1: Subjects with an RSV positive *nasal swab* during the study before time of sampling will be eliminated. Note that such subjects are removed from the analysis because they are infected by RSV; as a consequence their antibody levels are no longer maternal antibody levels.

STEP 2: Run the model and compute expected value based on the decay curve for each subjects

200150 (EPI-RSV-005 BOD)

Statistical Analysis Plan Amendment 1 Final

STEP 3: Subjects with an antibody titer at the sampling time that is more than 2-fold above the expected value based on their baseline (cord blood) value and the established decay curve will be considered to have been infected, eliminated and the decay curve refined.

STEP 4: Step 3 is repeated up to 5 times until the most accurate decay curve is established.

The natural decay of antibody will be determined using linear regression between the log of antibody level (Y) and time t (age in months) with subject as a random effect. Indeed, all subjects have RSV neutralizing antibodies measured at birth (cord blood). And, each subject of the Total sub-cohort will be randomly selected to be sampled for RSV neutralizing antibodies at one of the following time points: 2, 4, 6, and 12 months. For the natural decay model, subjects will have maximum 2 RSV neutralizing antibodies measures, one at birth and one either at 2 months or 4 or 6 or 12 months.

A table will describe the decay rate and half-life statistics of the natural decay model.

A descriptive table will describe the serology status (positive/negative) according to the natural decay analysis.

A sensitivity analysis of the decay curve will be explored in sub-sample consisting of the subjects born 'off-season' as these have the lowest likelihood of having been infected.

Please note that additional exploratory analysis could be perform depending on the data and that the decay analysis could be adapted depending on the number of samples < LLOQ for each time points, especially for the later time points. Specific analysis of the twins could be explored if the number of twins reaches at least 50 subjects. Additional models such as models including a t^2 term or some covariates could be explored.

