The measured maternal antibody levels by storage condition or tube type will be analysed graphically and by group statistics (mean, 95% CI). Group means will be compared by t-test to assess the statistical significance of differences.

The measured maternal antibody levels in samples collected 'according to recommended procedure' and 'not according to recommended procedure' will be analysed graphically and by group statistics (mean, 95% CI). Group means will be compared by t-test to assess the statistical significance of any difference.

• To assess the impact of potential RSV risk factors (e.g. complications at birth, family history of respiratory disease, lifestyle characteristics and household composition, breast feeding, passive smoking, day care attendance) on the incidence and severity of RSV-associated LRTI.

The incidence of any, severe, non-severe RSV-associated LRTI will be analysed using a Poisson regression model including potential risk factors.

• To assess the natural decay of maternal antibody levels using a single follow-up blood sample collected from a randomly selected sub-cohort of subjects at 2, 4, 6, 12, 18 and 24 months.

The primary analysis will be based on ATP sub-cohort for this objective.

The decay of maternal antibody levels over time will be analysed graphically and by a log-linear regression. A true, natural decay curve will be explored by stochastically reducing the sample to uninfected subjects only. The following steps will be taken to identify, confirmed and suspected infected subjects to eliminate these from the sample;

- Subjects with an RSV positive nasal swab during the study before time of sampling will be eliminated.
- A sensitivity analysis of the decay curve will be explored in sub-sample consisting of the subjects born 'off-season' as these have the lowest likelihood of having been infected.
- Subjects with an antibody titer at the sampling time that is more than 2-fold above the expected value based on their baseline (cord blood) value and the established decay curve will be considered to have been infected, eliminated and the decay curve refined.
- Step 3 is repeated up to 5 times until the most accurate decay curve is established.

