2. STUDY DESIGN

2.1. Design summary

In the primary study, subjects were to be followed-up from birth up to the age of 2 years for RSV LRTI. Episodes of wheeze and diagnoses of asthma were also documented.

Figure 1 Study design diagram for the primary study (from birth up to the age of 2 years for detection of RSV LRTI)

V = Visit; D = Day; M = Month

ICF = Informed Consent Form; CBS = Cord Blood Sample; NS = Nasal Swab; DC = Diary Card; BS = Blood Sample ¹ An examination visit (off-site/site) is to occur for new or worsened, potential LRTI case as identified during active or passive follow-up contact. The examination visit needs to occur as soon as possible and no later than 72 hours after the potential LRTI was identified during a follow-up contact. Each subject may have none, single or multiple examination visits over the course of the study.

² A sub-cohort of subjects will be randomized for a single blood draw to occur at one of the six possible time points and will have a Visit 3 corresponding to this time point (if still participating at that time); either V3a at 2, V3b at 4, V3c at 6, V3d at 12, V3e at 18 or V3f at 24 months.

* All follow up procedures associated with V2 (e.g. ICF) must be performed within 5 working days after birth.

200150 (EPI-RSV-005 BOD)

Statistical Analysis Plan Amendment 1 Final

- Type of design: Prospective, epidemiological, interventional, multi-country, cohort study.
- Study population:
 - A cohort of approximately 2400 infants will be included in the study at birth and followed-up up to 2 years of age.
 - A sub-cohort of subject will be randomized for a single blood draw to one of the time point at 2, 4, 6, 12, 18 or 24 months of age as described in Table 1.

Table 1Blood sample collection

Time point	Seroprevalence sub-cohort Number of allocated subjects*
2 months	200
4 months	200
6 months	250
12 months	300
18 months	450
24 months	600
Total	2000

Note: Only one blood sample will be withdrawn from each subject in this sub-cohort.

*Number of subjects selected per time point is calculated based on the required number of subjects for adequate analysis considering an accumulating drop-out of subjects. Actual numbers might be less due to drop-outs and exclusion of subjects with gestational age <36 weeks..

- Type of study: Self-contained.
- Data collection: Electronic case report form (eCRF).
- Biological samples (Primary Study only):
 - Cord Blood collected from all participating subjects, at birth.

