Descriptive analyses (seropositivity rate with 95% CIs, geometric mean, median, min, max) of RSV neutralizing antibodies at 2, 4, 6, 12, 18 and 24 months will be presented.

Prevalence of infection will be determined at the time of the analysis based on the measured antibody titer *vs*. the expected antibody level at the time of sampling based on the individual baseline (cord blood) value and the average, modelled decay rate for subjects with blood sampling at time point 2, 4, 6, and 12 month. RSV infection is defined as titers 2-fold higher than expected value. For subjects with blood sampling during second year of life, a sample with positive result will count as prevalence of infection.

All exact 95% CI will be two-sided, based on the Clopper-Pearson based on a mathematical relationship (see Fleiss et al (2003), p. 25) between the F distribution and the cumulative binomial distribution.

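### The fixed 2-fold cut in the antibody decay model is not tied to titre scatter, so it over-corrects the decay curve and overstates RSV infection prevalence at months 2 to 12

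*SAP*

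**What the plan says.** The decay model is a log-linear regression: "The natural decay of antibody will be determined using linear regression between the log of antibody level (Y) and time t (age in months"), with a random subject effect and at most two titres per child. On the data used: "The analysis will be based on total sub-cohort subject with blood sampling at month 2, 4, 6, and 12 for this objective".

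Step 1 takes out known infections: "Subjects with an RSV positive *nasal swab* during the study before time of sampling will be eliminated". Step 3 then treats as infected, and removes, "Subjects with an antibody titer at the sampling time that is more than 2-fold above the expected value based on their baseline" cord titre and the fitted curve. Step 4 reads "Step 3 is repeated up to 5 times until the most accurate decay curve is established". Nothing defines accuracy, and nothing links the 2-fold limit to assay error or to differences between children. Protocol 9.7.3 has the same rule: such children "will be considered to have been infected, eliminated and the decay curve refined".

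The curve then serves a secondary objective. In SAP 6.9.2 the expected titre at months 2 to 12 is the child's own cord titre carried down the average modelled decay, and "RSV infection is defined as titers 2-fold higher than expected value". Template 52 counts infections in the same way. Table 9 agrees for RSV-A, but labels RSV-B infected at or above 1 x expected.

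**The concern.** The ratio of follow-up titre to expected titre carries error from two titres plus individual differences in decay rate. Uninfected children therefore lie on both sides of a correct curve. A fixed cut on the high side catches infected children and also the upper tail of the uninfected. Refitting without that tail steepens the curve, which moves further uninfected children over the limit at the next pass. The same cut on the lowered curve then becomes the case definition for prevalence.

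Two reported results are at stake: the half-life of maternal antibody (tertiary) and the prevalence of infection at months 2 to 12 (secondary). The Clopper-Pearson interval planned in SAP 6.9.2 reflects sampling error only, so an inflated prevalence would carry an interval that takes no account of misclassification.

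**Working it through.** The plan states no half-life, titre scatter or expected prevalence for this analysis, so there is no figure to reproduce.

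**Inputs from the documents.** Allocation from SAP Table 1 is 200, 200, 250 and 300 children at months 2, 4, 6 and 12, which makes 950. The deletion rule, up to five repeats and the infection label are in SAP 6.9.2 and 6.9.3. The RSV-A cut-off is 8, with 4 substituted below it for GMT calculation (SAP Table 7).

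**Assumptions.** Half-life 1.0 to 1.5 months. SD of log10(observed/expected) in uninfected children, *s*, of 0.10 to 0.40. Normal scatter.

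**1. The cut alone, on a correct curve.** Two-fold is log10(2) = 0.301, so the false-label share is 1 − Φ(0.301/*s*):
- *s* = 0.10: 0.301/0.10 = 3.01, giving 0.1%
- *s* = 0.20: 0.301/0.20 = 1.505, giving 6.6%
- *s* = 0.30: 0.301/0.30 = 1.003, giving 15.8%

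**2. Adding the loop, nobody infected.** Steps 2 to 4 were simulated 300 times per setting, with no titre below the cut-off. Positive slope error means decay too steep.

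| *s* | Labelled, cut alone | Labelled, after loop | Slope error |
|---|---|---|---|
| 0.10 | 0.1% | 0.1% | 0.0% |
| 0.15 | 2.2% | 2.4–2.5% | +0.4 to +0.5% |
| 0.20 | 6.6% | 8.6% | +1.3 to +2.0% |
| 0.30 | 15.8% | 27% | +5.7 to +8.5% |
| 0.40 | 22.6% | 45% | +13 to +19% |

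The cut itself accounts for 6.6/8.6 = 77% of false labels at *s* = 0.20 and 15.8/27 = 59% at 0.30; the loop adds the rest. At *s* = 0.40 and true half-life 1.20, successive fits give 1.20, 1.12, 1.08, 1.06, 1.04 and 1.03 months, so the curve is still moving at the fifth pass.

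**3. Scatter that grows with age.** Take half-life 1.25 months (0.8 log2 per month), error SD *e* log2 per titre and CV *c* of individual decay rates. The SD of the log2 ratio at month *t* is √(2*e*² + (0.8*ct*)²). With *e* = 0.5 and *c* = 0.10:
- month 2: √(0.50 + 0.0256) = 0.725; 1 − Φ(1/0.725) = 8%
- month 4: √(0.50 + 0.1024) = 0.776; 10%
- month 6: √(0.50 + 0.2304) = 0.855; 12%

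After the loop these become about 11, 17 and 23%, and half-life falls to 1.16 (1.16/1.25 − 1 = −7.2%). With *e* = 0.35 and *c* = 0, false labels are only 2.3 to 2.6%. Across these settings half-life falls to between 1.16 and 1.24 months, a shortening of about 1 to 7%.

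**4. With infections that the swabs missed.** Assume 5, 10, 20 and 40% at months 2, 4, 6 and 12, with a mean 8-fold rise. Overall prevalence is (10 + 20 + 50 + 120)/950 = 21%.
- No deletion: slope about 12% too shallow.
- Loop as planned, *s* = 0.10, 0.20, 0.30, 0.40: slope error −0.1, +1.5, +6.8, +14.8%; prevalence 20.6, 26.8, 40.4, 53.5%.
- Symmetric 2-fold trimming: slope 3 to 10% too shallow.
- Two-component mixture without deletion: slope within 0.4%; prevalence 20.3 to 21.3%. With nobody infected, slope error is at most 1.8% and estimated prevalence 0.1 to 7.5%.

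**5. Titres below the cut-off.** With an assumed cord GMT of 1000 and half-life 1.2 months, the expected month-12 titre is 1000 × 2^−10 = 0.98. If the substituted value of 4 were carried into this comparison, an undetectable titre would be 4/0.98 = 4.1 times expected and labelled infected. Simulated that way, net slope error is −3.5% to +1.6% for *s* of 0.10 to 0.30, yet 72 to 81% of uninfected month-12 children are labelled infected. At months 2, 4 and 6 the false labels are 5.9, 5.3 and 4.3% at *s* = 0.20, and 16.4, 16.6 and 17.8% at *s* = 0.30.

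**6. RSV-B as Table 9 has it.** At 1 x expected, half of uninfected children lie above a correct curve. After the loop the share is about 50% at *s* = 0.10 and 55 to 73% at 0.20 to 0.40.

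**The case against.** The best defence is that upward deletion is deliberate. The aim is to leave only uninfected children, and infection raises titres. Protocol 1.1.1 cites infection in 50 to 70% of infants in the first year, so a population with no infection is a device for isolating the error, not a forecast. Left untrimmed, the curve would be too shallow (item 4). This stands: one-sided removal is not in itself the fault, and a reader who infers that deleting low titres as well would cure the problem would make the decay estimate worse.

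Second, the size rests on scatter that the documents do not supply, and at *s* = 0.10 the rule does no harm. That also stands.

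Third, Template 50 tabulates the sequential fits, so drift in the half-life would be visible, and SAP 6.9.3 allows adaptation for samples below the LLOQ and further exploratory models. This helps only in part. Template 52 does not show prevalence by pass, and none of the permitted extras is specified to vary the cut. The one named sensitivity analysis, in children born off-season, leaves the rule as it is. It also relies on a Northern season of April to September (SAP 6.1.4.5), against October to March in Protocol 1.1.1; those passages must be reconciled.

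Fourth, the analyses are descriptive, and raw GMTs and seropositivity are reported regardless (Template 47). This bears on severity, not on direction.

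**Conclusion.** The point holds in direction and is conditional in size. The fixed cut and the loop together over-correct the curve downward and overstate prevalence at months 2 to 12 unless uninfected scatter is small: negligible at SD 0.10 log10, about 9% false labels at 0.20 and 27% at 0.30 with nobody infected. Those overall figures assume normal scatter and no titre below the cut-off. Half or more of the false labels come from the cut, not from the repetition.

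Three stronger readings are tempting and not supported. A reader might infer that early prevalence will be mostly false positives; the documents give no scatter from which to conclude that. A reader might infer that the loop always runs to a fifth pass; the text sets a maximum only. And a reader might quote a month-12 false-positive rate from a model without a floor; with a half-life of 1.25 months, titres fall 2^9.6 = 776-fold by month 12, so every RSV-A cord titre would have to exceed about 776 × 8 = 6,200.

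Severity: should be fixed. The objectives affected are secondary and tertiary, and no co-primary result is touched.

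**What to change.** Replace Steps 3 and 4 of SAP 6.9.3 with a two-component (uninfected/infected) mixture for the log ratio of follow-up to cord titre. Let the uninfected SD vary by time point, and treat titres below the cut-off as censored. Take the decay rate and the prevalence at months 2, 4, 6 and 12 from that model, with intervals from it too. Keep the iterative 2-fold rule as a sensitivity analysis, with a stated stopping criterion. Do not substitute symmetric trimming.

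In the same edit, reconcile the RSV-B rows of Table 9 with the 2-fold rule in SAP 6.9.2 and Template 52.

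The cost is SAP wording and modest programming, with no new data. The estimates will depend on the assumed mixture form. The simulated data had that form, which favours the method, and the mixture still returned up to 7.5% prevalence with nobody infected. The censored version was not simulated and should be tried on the planned allocation before adoption.

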6.10. Analysis of other viruses and RSV infection

6.10.1. Analysis of tertiary objective: incidence of other respiratory viruses as cause of LRTI and severe LRTI

The number and percentage of cases for each respiratory virus identified for all WHO LRTI and WHO severe LRTI. For each respiratory virus infection, number and percentage will be summarized by single or co-infection status.

The number and percentage of cases associated with each of the other respiratory viruses, with at least one other a respiratory virus, 1, 2, or more than 2 additional viruses, will be described for WHO LRTI and WHO severe LRTI.

The percentage will be computed using the number of cases (associated with each of the other respiratory viruses, with at least one other a respiratory virus, 1, 2, or more than 2 additional viruses) divided by the total number of case for a given endpoint.

This analysis will be performed at less than 3 month, between 3 - 5 month, 6 - 11 month, and 12 - 23 months and by country.

Statistical Analysis Plan Amendment 1 Final

Other respiratory viruses include Influenza A (subtypes H1 and H3); Influenza B; Parainfluenza virus type 1, 2, 3, and 4; Human Metapneumovirus; Rhinovirus/Enterovirus; Adenovirus; Bocavirus and Coronavirus - 229E, OC43, NL63, HKU1. The analyses will be performed for each viral type and aggregated viral types, for example, viral type of parainfluenza will combine parainfluenza virus type 1, 2, 3 and 4.

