11.2.1.4. LRTI

11.2.1.4.1. Any LRTI (WHO definition)

The subject will be defined as LRTI positive according to WHO definition when he is presenting:

- history of cough or difficulty breathing,
- and a measured oxygen saturation < 95% or an increase of respiratory rate.

200150 (EPI-RSV-005 BOD)

Statistical Analysis Plan Amendment 1 Final

For derivation purposes we are characterizing 2 groups of items:

- Component A which gathers items used to derive history of cough and difficulty breathing,
- Component B which gathers the oxygen saturation and respiratory rate.

Component A:

The subject will be considered positive for Component A when one or several of the following items are reported in interview during the examination visit:

- Cough reported in interview during the examination visit or Dica (fields [EXAM_VS.SYMP_CAT]="Cough" and [EXAM_VS.SYMP_REP]="Y")
- And/or difficulty breathing as defined in section 11.2.2.1

Please note that the 2 symptoms: blocked nose and runny nose are not considered here for the derivation, indeed even if in the table 1 note 1 the case definition mentioned "Based on history reported by parents/LARs and includes difficulty breathing associated with nasal obstruction". (in fact it relates to how the data is intended to be collected in future trials where the mother is asked does the child have difficulty breathing yes or no. It is meant to qualify that if the child's breathing difficulty is due to only blocked nose if the mother says its difficulty breathing it is. However, in this study we don't have the question difficulty breathing and so we cannot know whether the blocked nose was or not associated with difficulty breathing in the mothers view)

Component B:

The subject will be considered positive for Component B when one or both of the following statement is reached:

- Blood Oxygen Saturation <95% (field [CLN_SGN2.BLSAT_V])
- And/or Increased Respiratory rate as defined in section 11.2.2.2

Please note that Blood Oxygen Saturation and respiratory rate are measured during the examination visit.

The subject will be defined as LRTI positive according to WHO definition when he is positive for Component A AND positive for Component B.

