12.7. Other viruses and RSV infection

12.7.1. Tertiary other viruses and RSV infection analysis

12.7.1.1. (TO) To explore the association of RSV and other respiratory viruses with the incidence of LRTI and/or severe LRTI (as determined by the LRTI case definition and severity scale) using xTAG[™] RVP Fast assay.

Template 53 The occurrence of respiratory viral infections, by cause, identified in cases [WHO LRTI – WHO severe LRTI – WHO RSV LRTI, WHO RSV severe LRTI] in the first two year of life, overall and by country (PPS)

		Age Group				
		0 - 2 month	3 – 5 month	6 – 11 moth	12 - 23 month	Total
		N = xx	N = xx	N = xx	N = xx	N = xx
Country	Respiratory virus identified					
	Influenza A/H1, n(%)	n (%)	n (%)	n (%)	n (%)	n (%)
	Influenza A/H3, n(%)	n (%)	n (%)	n (%)	n (%)	n (%)
	Influenza B, n(%)	n (%)	n (%)	n (%)	n (%)	n (%)
	Influenza, n(%)	n (%)	n (%)	n (%)	n (%)	n (%)
	Parainfluenza virus type 1, n(%)	n (%)	n (%)	n (%)	n (%)	n (%)
Overall	Parainfluenza virus type 2, n(%)	n (%)	n (%)	n (%)	n (%)	n (%)
	Parainfluenza virus type 3, n(%)	n (%)	n (%)	n (%)	n (%)	n (%)
	Parainfluenza virus type 4, n(%)	n (%)	n (%)	n (%)	n (%)	n (%)
	Any Parainfluenza virus, n(%)	n (%)	n (%)	n (%)	n (%)	n (%)
	Rhinovirus, n(%)	n (%)	n (%)	n (%)	n (%)	n (%)
	Adenovirus, n(%)	n (%)	n (%)	n (%)	n (%)	n (%)
	Bocavirus, n(%)	n (%)	n (%)	n (%)	n (%)	n (%)
	Coronavirus 229E, n(%)	n (%)	n (%)	n (%)	n (%)	n (%)
	Coronavirus OC43, n(%)					
	Coronavirus NL63, n(%)					
	Coronavirus HKU1, n(%)					
	Any Coronavirus, n(%)					
	[RSVA (RT-qPCR), n(%)]					
	[RSVB (RT-qPCR), n(%)]					
<each< td="">						</each<>						

 Country>
 Image: N = Total number of [all – RSV positive] cases with [WHO LRTI – WHO severe LRTI] at given age interval

n = number of [WHO LRTI – WHO severe LRTI] cases positive for a given viral infection

% = n/N

LL, UL for percentage = Exact 95% Lower and Upper confidence limits

Note:

Infection with other respiratory viruses is determined using xTAG[™] RVP Fast assay

200150 (EPI-RSV-005 BOD)

Statistical Analysis Plan Amendment 1 Final

Template 54 Frequency of respiratory viral co-infections identified in WHO [LRTI - severe LRTI – RSV LRTI – RSV severe LRTI] the first two years of life, overall and by country (PPS)

		Age Group				
		0 - 2 month	3 – 5 month	6 – 11 moth	12 - 23 month	Total
		N = xx	N = xx	N = xx	N = xx	N = xx
Country	Co-infection					
	No co-infection	n (%)	n (%)	n (%)	n (%)	n (%)

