	1 other virus	n (%)	n (%)	n (%)	n (%)	n (%)
Overall	2 other viruses	n (%)	n (%)	n (%)	n (%)	n (%)
	>2 other virus	n (%)	n (%)	n (%)	n (%)	n (%)
By country						

N = Total number of WHO [LRTI – severe LRTI] cases at given age interval

n = number of WHO [LRTI - severe LRTI] cases for a category of other viral infection

% = n/N

LL, UL for percentage = Exact 95% Lower and Upper confidence limits Note:

Infection with other respiratory viruses is determined using xTAG[™] RVP Fast assay

Template 55 Viral single and co-infections among all WHO [LRTI – severe LRTI] cases, (PPS)

	ALL	Single infection	Co – infection
	N =	N =	N =
Respiratory virus identified			
Influenza A/H1, n(%)	n(%)	n(%)	n(%)
Influenza A/H3, n(%)	n(%)	n(%)	n(%)
Influenza B, n(%)	n(%)	n(%)	n(%)
influenza, n(%)	n(%)	n(%)	n(%)
Parainfluenza virus type 1, n(%)	n(%)	n(%)	n(%)
Parainfluenza virus type 2, n(%)	n(%)	n(%)	n(%)
Parainfluenza virus type 3, n(%)	n(%)	n(%)	n(%)
Parainfluenza virus type 4, n(%)	n(%)	n(%)	n(%)
Any Parainfluenza virus, n(%)	n(%)	n(%)	n(%)
Rhinovirus, n(%)	n(%)	n(%)	n(%)
Adenovirus, n(%)	n(%)	n(%)	n(%)
Bocavirus, n(%)	n(%)	n(%)	n(%)
Coronavirus 229E, n(%)	n(%)	n(%)	n(%)
Coronavirus OC43, n(%)	n(%)	n(%)	n(%)
Coronavirus NL63, n(%)	n(%)	n(%)	n(%)
Coronavirus HKU1, n(%)	n(%)	n(%)	n(%)
Any Coronavirus, n(%)	n(%)	n(%)	n(%)
RSVA (RT-qPCR) , n(%)	n(%)	n(%)	n(%)
RSVB (RT-qPCR) , n(%)	n(%)	n(%)	n(%)

N = number of [WHO LRTI, WHO severe LRTI] cases in single infection, co-infection, and overall categories

n = number of WHO [LRTI - severe LRTI] cases for respiratory virus identified

Note:

RSV infection is determined using RT-qPCR

Infection with other respiratory viruses is determined using xTAG[™] RVP Fast assay

^{% =} n/N

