Template 64 Number and percent of examination visit by nasal swab collection status, overall and by country (PPS)

	Tota N =	al	AR N =		BD N =		CA N =		FI N =		HN N =		SA N =		TH N =		US N =	
Nasal swabs	n	%	n	%	n	%	n	%	n	%	n	%	n	%	n	%	n	%
Yes																		
Not done, refused																		
Not done, other																		

N = Total number of examination visit in given country

n = number of visits with swab collection in the given category

% = n/N

AR = Argentina

BD = Bangladesh

CA = Canada

FI = Finland

HN = Honduras

SA = South Africa TH = Thailand

US = US

Template 65 Number and percent of examination visit by number of days between onset of [cough or difficulty breathing – cough – difficulty breathing] and follow up examination visit, overall and by country (PPS)

	Tota N =	I	AR N =		BD N =		CA N =		FI N =		HN N =		SA N =		TH N =		US N =	
	n	%	n	%	n	%	n	%	n	%	n	%	n	%	n	%	n	%
If yes, time between onset of symptom and examination visit (days)																		
Same day as exam visit																		
1																		
2																		
3																		
4 - 6																		
>6																		

N = Total number of examination visit in a given country with onset of [cough or difficulty breathing – cough – difficulty breathing] reported

n = number of examination visits for which onset of [cough or difficulty – cough – difficulty breathing] occurred for a given category

% = n/N

AR = Argentina

BD = Bangladesh

CA = Canada

FI = Finland

HN = Honduras

SA = South Africa

TH = Thailand

US = US

200150 (EPI-RSV-005 BOD)

Statistical Analysis Plan Amendment 1 Final

Template 66 Descriptive statistics of total RSV viral load by number of days between any symptom apparition and nasal swab collection calculated for first [WHO RSV-LRTI – WHO RSV Severe LRTI] episodes (PPS)

			Num	ber f	irst (N=	episode		
Number of days from onset of any symptom until swab collection	n	Mean	95% CI	SD	Q1	Median	Q3	Min/Max
Same day as onset of symptom								
1								
2								
3								
4 – 6								
>6								

N = Total number of [WHO RSV-LRTI – RSV Severe LRTI] episodes

n= Number of first episodes swabbed for a given category

SD=Standard Deviation

Q1 and Q3 = 1^{st} and 3^{rd} quartiles

Min/Max = Minimum/Maximum

Total RSV viral load computed as RSV A Viral load + RSV B Viral load

Note:

There may have been multiple swabs or examination visits for an episode. In such cases, the swab with highest viral load was considered for this analysis

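### Virus and co-infection percentages are divided by all LRTI cases instead of cases with a valid RVP result, so virus-positive shares are understated whenever cases are untested

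*SAP*

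**What the plan says.** SAP 6.10.1 covers the other respiratory viruses found in WHO LRTI and WHO severe LRTI. The number of cases with a given virus, or with a given number of additional viruses, is "divided by the total number of case for a given endpoint". The results are split by country and into four age bands (under 3, 3-5, 6-11 and 12-23 months).

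The shells in SAP 12.7.1 follow this rule:

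- Template 53 (viruses by cause): "N = Total number of [all – RSV positive] cases with [WHO LRTI – WHO severe LRTI] at given age interval".
- Template 54 (co-infections): "N = Total number of WHO [LRTI – severe LRTI] cases at given age interval". Its rows are "No co-infection" and one, two or more than two other viruses. There is no row for a case without a result.
- Template 55 (single versus co-infection) uses column denominators: "cases in single infection, co-infection, and overall categories".

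SAP 6.10.2, on co-infections with RSV, names no denominator.

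The all-cause endpoint needs no virology. SAP 11.2.1.4.1 reads "The subject will be defined as LRTI positive according to WHO definition when he is positive for Component A" and for Component B. These components are reported cough or difficulty breathing, and low oxygen saturation or raised respiratory rate at the examination visit. SAP 12.8.2, Template 64, tabulates examination visits by swab status and includes rows for swabs refused and swabs not done for other reasons.

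**The concern.** A case without a swab, or with a swab but no valid RVP result, can enter the denominator but can never enter a virus numerator. The reported share then mixes how often the virus was present with how often anyone looked for it. Because the tables are split by country and age band, uneven swab or assay completion would look like a difference in virus epidemiology.

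The SAP handles missing data differently elsewhere. Template 40 counts only subjects with available serology. Templates 43 to 45 drop subjects with missing cord blood values. Templates 4 and 17 carry rows for missing data. The virus tables do none of this.

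Two tertiary objectives rest on these percentages: the association of RSV and other viruses with LRTI, and that of co-infections with RSV LRTI.

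**Working it through.** The plan gives no virus percentage and no count of untested cases, so there is no stated figure to reproduce. The check is algebra with assumed inputs.

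**Inputs**

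- Denominator: all cases of the endpoint (SAP 6.10.1, Templates 53 and 54).
- u, the share of cases without a valid RVP result: not in the documents; assumed 5, 10 and 20%.
- p, the share of tested cases positive for a given RVP virus: assumed 30%.
- q, the share of tested cases without co-infection: assumed 60%.

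**Step 1. RVP viruses, and the rows for 1, 2 or more than 2 other viruses.** Reported share = p(1-u).

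**Step 2. The no-co-infection row of Template 54.** The SAP does not say where an untested case goes, so there are two possibilities. If it goes into this row, the reported share is q(1-u) + u. If it goes into no row, the share is q(1-u), and the four rows add up to 1-u.

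| u | Virus, true 30% | No co-infection, true 60%: untested counted there | No co-infection, true 60%: untested in no row | Sum of rows in the last case |
|---|---|---|---|---|
| 5% | 28.5% | 62.0% | 57.0% | 95% |
| 10% | 27.0% | 64.0% | 54.0% | 90% |
| 20% | 24.0% | 68.0% | 48.0% | 80% |

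**Step 3. The same in counts.** Assume 200 cases, 20 of them untested. Of the 180 tested, 72 have at least one other virus and 108 have none.

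- At least one other virus: 72/200 = 36.0% as planned; 72/180 = 40.0% among tested cases.
- No co-infection: (108 + 20)/200 = 64.0% or 108/200 = 54.0% as planned, depending on the unstated rule; 108/180 = 60.0% among tested cases.

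**Step 4. Template 55.** The overall column is diluted as in Step 1. The co-infection column contains only cases with detected viruses, so untested cases do not dilute it. The single-infection column can shift. As a separate illustration, take 108 single infections among fully tested cases, 40 of them RSV. If 8 further cases are RT-qPCR positive without an RVP result and are classed as single infections, the RSV share moves from 40/108 = 37.0% to 48/116 = 41.4%.

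**Step 5. RSV rows.** RSV-A and RSV-B come from RT-qPCR. A missing RVP run leaves them unchanged. A missing or invalid swab or RT-qPCR result dilutes them, but only in all-cause LRTI, because an RSV LRTI case has a positive RT-qPCR result by definition (SAP 11.2.1.6).

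**Step 6. Spurious country contrast.** Take two countries with the same true share of 30%, and assume u = 2% in one and 20% in the other. They would show 0.30 x 0.98 = 29.4% and 0.30 x 0.80 = 24.0%, an apparent gap of 5.4 points.

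**The case against.** The strongest reply is that few cases may be untested. WHO LRTI requires measurements made at an examination visit. Protocol 6.5.16 and Appendix E call for a swab at every such visit, whether or not LRTI is confirmed. Protocol 6.7.3 lists the RVP assay for nasal swabs without restricting it to selected ones. An episode can combine several visits and swabs, so one missed swab need not leave a case untested. For RSV LRTI a positive swab exists by definition, so only the RVP run can be missing. Template 64 already shows swab completion by country. The analyses are tertiary and descriptive, and the co-primary RSV incidence is untouched.

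All of this stands as a limit on size. It does not repair the rule. Template 64 shows that full completion is not taken for granted. That template counts visits rather than cases, has no age split and says nothing about failed or missing RVP runs. RVP results also arrive in a separate, second database freeze (SAP 8.1), so RT-qPCR and RVP completeness can differ.

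Two stronger readings are tempting. A reader might infer that every percentage in these tables is too low. That is wrong: the no-co-infection row rises if untested cases are put there, RSV rows survive a missing RVP run, and Template 55's co-infection column is not diluted. A reader might also infer that the SAP classes untested cases as virus-negative and free of co-infection. It does not say so; this is only a guess from the absence of another row.

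**Conclusion.** The concern holds in this limited form. The denominator in SAP 6.10.1 and Templates 53 and 54 is all cases, with no restriction to tested cases and no row for the rest. Whenever u is above zero, the all-case RVP-virus percentages and the percentages with 1, 2 or more than 2 other viruses are understated by the factor (1-u). For a true 30%, that is 1.5, 3 or 6 points at u = 5, 10 or 20%. The no-co-infection share is distorted upward or downward, depending on a rule the SAP leaves open. RSV single infection in Template 55 may be overstated.

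The size rests on assumed values of u, since the documents give none; at u = 0 there is no bias. The (1-u) factor takes the share among tested cases as the true share, which requires untested cases to resemble tested ones. For RSV LRTI the exposure is smaller and partly inferred: section 6.10.2 names no denominator, and Template 54's footnote names only LRTI and severe LRTI, although its title also covers RSV LRTI. The point should be corrected because it changes reported results at almost no cost, but it does not bear on the co-primary objectives.

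**What to change.** In SAP 6.10.1, 6.10.2 and Templates 53 to 55:

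- Define N for RVP viruses as cases with a valid RVP result from at least one swab of the episode.
- Define N for the RSV-A and RSV-B rows as cases with a valid RT-qPCR result.
- Require both results before assigning single-infection or co-infection status, and fill the no-co-infection row from such cases only.
- Add a count of cases not tested or without a valid result, by country and age group. This lets the reader judge whether differences follow test completion and how far the tested cases can stand for all cases.

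The cost is a few lines of SAP wording and one extra table row. No further data are needed. If every case was tested, the results do not change and the new row shows it.
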